8.2.5 Other Efficacy Endpoints

The remaining efficacy analyses will present further presentations of the itch intensity measures, itch-related quality-of-life measures, plus the PGIC.

8.2.5.1 Itch Intensity Measures

- Proportion of subjects who have an improvement from baseline at Week 12 of the Double-Blind Treatment Period with respect to the weekly mean of the 24-hour Worst Itching Intensity NRS scores >0 , ≥ 1 , ≥ 2 , ≥ 3 , ≥ 4 , ≥ 5 , and ≥ 6 will be analyzed and reported in a manner identical to that described in section 8.2.4.3 above. The same dataset from the primary analysis will be used, utilizing additional flags for these cut points of improvement. However, no adjustment for interim analysis will be implemented.
- Proportion of subjects who have an improvement from baseline at Week 12 of the double-blind treatment period with respect to the weekly mean of the 24-hour Worst Itching Intensity NRS scores ≥ 3 will be reported overall and by each of the randomization stratification variables using the primary analysis and model removing the stratification factor that's being reported from the model. The same dataset from the primary analysis will be used, utilizing additional flags for these cut points of improvement. However, no adjustment for interim analysis will be implemented.
- Proportion of subjects that are complete responders will be reported. A subject that has $\geq 80\%$ of the non-missing 24-hour Worst Itching Intensity NRS scores equal to 0 or 1 on Week 12 is considered a complete responder; subjects that have less than 4 NRS scores reported or drop out prior to week 12 are also considered non-responders. Differences between CR845 0.5 mcg/kg and placebo will be compared using a logistic regression model containing terms for treatment group,

baseline NRS score, use of anti-itch medication during the week prior to randomization, and presence of specific medical conditions.

- Change from baseline in the weekly mean of the 24-hour Worst Itching Intensity NRS score at each week of the Double-blind Treatment Period (Week 1 to Week 12). Treatment differences between CR845 and placebo at each post-baseline time point will be analyzed using an MMRM. The model will contain treatment, week, and treatment-by-week interaction as fixed effects, and baseline score and the randomization stratification variables as covariates.

An unstructured covariance matrix will be used to model the within-subject errors. Should the model fail to converge, a compound symmetric covariance matrix will be used instead. The Kenward-Roger approximation will be used to estimate the denominator degrees of freedom. Two analyses will be conducted: in the first analysis; missing scores will not be imputed, and in the second analysis, the same dataset from the primary analysis will be used to address missing data. Standard descriptive statistics will be reported for each time point on the values and changes from baseline along with the LS means, standard errors, 95% CIs, and differences between treatment groups reported with LS means, standard errors, and 95% CIs.

8.2.5.2 Itch-related Quality-of-Life Measures

In addition to the Week 12 results and treatment comparisons, all time points for the 5-D Itch Scale and Skindex-10 will be reported as described in Section [8.2.4.3](#), with the exception of the ANCOVA analysis, and utilized as further efficacy endpoints.

Additionally, the ANCOVA and MMRM analyses described in Section [8.2.4.3](#) for the Skindex-10 will be repeated for all 3 of the Skindex-10 subdomains and the 5 Itch 5-D domains.

The proportion of subjects who have an improvement from baseline in Skindex-10 score of at least 15 points by week will be analyzed and reported along with a logistic regression model-based estimates of the proportions of responders, odds ratio, 95% CIs, and p-value. No imputation of data will be implemented.

The proportion of subjects who have an improvement from baseline in the 5D Itch Scale total score of at least 5 points by week will be analyzed and reported along with a logistic regression model-based estimates of the proportions of responders, odds ratio, 95% CIs, and p-value. No imputation of data will be implemented.

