4.2 Intent-to-treat Population

The ITT Population is defined as the group of subjects who are randomized to a treatment group. Following the ITT principle, subjects in the ITT Population will be analyzed according to their randomized treatment, regardless of the actual treatment received. The ITT population will be used to analyze all efficacy endpoints collected during the double-blind phase.

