8.2.4.3 Key Secondary Analyses

5-D Itch Scale and the Skindex-10 Scale

The 5-D Itch Scale and the Skindex-10 Scale scores will be analyzed only at Week 12 using an analysis of covariance (ANCOVA). The model will contain treatment as fixed effects, with baseline score and the randomization stratification variables as covariates. The baseline 5-D total score and the Skindex-10 total score will be defined as the value collected on Day 1, prior to randomization. This is a change from the final protocol dated 21DEC2017 and is being implemented to address the FDA advice received on 10JAN2019 stating that “*the analysis [of continuous efficacy endpoints] should be based on only data from one timepoint (e.g. Week 12); however, modeling approaches using all timepoints may be used as supportive analyses.*”

Additionally, subjects who discontinue treatment but continue on study and have 5-D and Skindex-10 scores recorded will have these scores censored following discontinuation of treatment; missing data rules will apply to these censored values as though they had missing values/ dropped out from the study entirely.

For each domain in each questionnaire, missing values at Week 12 will be imputed using an MI approach, assuming that subjects who discontinue double-blind treatment early would have similar 5-D Itch and Skindex-10 scores as other subjects in their respective treatment arm that have complete data. All available visits will be included in the MI to

better inform the Week 12 imputed results. The MI approach will proceed as follows, using all ITT subjects (that is, it will not be split into IA subjects and post- IA subjects):

- Intermittent missing scores will first be imputed using the Markov Chain Monte Carlo (MCMC) method implemented with the SAS MI procedure, which is appropriate for non-monotonic missing data.
- The monotone missing values will then be multiply imputed with the SAS MI procedure using the monotone regression method.
- For each stage, MI will be performed within treatment group with covariates for baseline score, both randomization stratification factors, and all non-missing visit scores for each domain of the questionnaire. Should convergence issues occur due to small cell size for the categorical covariates at either stage, they will be removed from the model.
- Twenty imputations will be performed for each domain.

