- For each questionnaire, the total score at each visit will be computed from the domain scores for each imputed dataset.
- The ANCOVA analysis described above will be implemented for each imputed dataset.
- Results of the ANCOVA on the multiply imputed data sets will be summarized by the SAS MIANALYZE procedure.

Since the observed change from baseline at Week 12 among the non-imputed data will be reported with the MMRM analyses described below, only the LS means, standard errors, 95% CIs, and differences between treatment groups reported with LS means, standard errors, and 95% CIs from the ANCOVA on the imputed data will be reported. The analysis will be completed for both the ITT and PP Populations.

Additionally, the 5-D Itch Scale and the Skindex-10 Scale scores will be analyzed using a mixed effects model with repeated measures (MMRM). The model will contain treatment, week, and treatment-by-week interaction as fixed effects, and baseline score and the randomization stratification variables as covariates. The baseline 5-D total score and the Skindex-10 total score will be defined as the value collected on Day 1, prior to randomization. Repeated measures will include values assigned at the end of Weeks 4, 8, 10, and 12 (end of treatment); see Section [3.1](#) for visit windowing.

It is important to note that, in HD subjects, the study drug administered during the last dialysis of a particular week is not cleared until the first dialysis of the next week. Therefore, measurements that would reflect treatment effect at the end of a specific week (e.g., Week 4) and labelled “end of Week xx” will actually be collected during the first day of the next week (e.g., Week 5).

An unstructured covariance matrix will be used to model the within-subject errors. Should the model fail to converge, a compound symmetric covariance matrix will be used instead. The Kenward-Roger approximation will be used to estimate the denominator degrees of freedom. Missing scores will not be imputed. Assuming that the data are

MAR, the estimates of the treatment differences calculated from the MMRM described above are unbiased.

Standard descriptive statistics will be reported for each time point on the values and changes from baseline along with the least squares (LS) means, standard errors, 95% CIs and differences between treatment groups reported with LS means, standard errors, and 95% CIs.

Worst Itching Intensity ≥ 4 -Point Improvement

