The proportion of subjects achieving ≥ 4 -point improvement from baseline with respect to the weekly mean of the daily 24-hour Worst Itching Intensity NRS at Week 12 of the Double-blind Treatment Period will be analyzed following a methodology identical to the one employed for the primary analysis of the primary endpoint (see section 8.2.2). The same dataset will be utilized; separate flags for various cut points of improvement will be utilized to facilitate these analyses. The analysis will be completed for both the ITT and PP Populations.

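### The by-week Skindex-10 (≥15-point) and 5-D Itch (≥5-point) responder analyses have no missing-data rule beyond not imputing, although imputed totals at each visit are already specified

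*SAP*

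**What the plan says.** SAP 8.2.5.2 defines two responder endpoints. For the first, "The proportion of subjects who have an improvement from baseline in Skindex-10 score of at least 15 points by week will be analyzed" by logistic regression, with estimated proportions, odds ratio, confidence interval and p-value. The second, a 5-point improvement in the 5-D total, is worded in parallel. Each paragraph ends with the same rule: "No imputation of data will be implemented". Neither states a denominator, a non-responder convention or the model covariates.

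SAP 8.2.4.3 treats the same two totals differently. Scores recorded after treatment stops are censored and handled as missing. Domain scores are then imputed within arm from all available visits: "The MI approach will proceed as follows, using all ITT subjects", and "Twenty imputations will be performed for each domain". Finally, "For each questionnaire, the total score at each visit will be computed from the domain scores for each imputed dataset". The ANCOVA on these data is the main Week 12 analysis. An MMRM without imputation supports it.

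The NRS responder endpoints account for dropouts. For the 4-point endpoint, SAP 8.2.4.3 reuses the primary analysis dataset, and "separate flags for various cut points of improvement will be utilized to facilitate these analyses". SAP 8.2.5.1 does the same for the other NRS cut-points and counts dropouts as non-responders for complete response.

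**The concern.** With no imputation and no non-responder rule, the natural reading is an observed-case model at each visit. Two groups drop out of it: subjects at visits after they stopped study drug, and subjects still on drug whose questionnaire is incomplete. Under SAP 8.2.4.2 a single missing Skindex-10 item makes the total missing. SAP 8.2.4.1 applies a similar rule to 5-D, except within the disability domain.

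The estimated response rate then describes those still observed. If stopping is related to how a subject was doing, and the two arms lose different kinds of subject, the comparison is distorted. At stake is the interpretation of the only responder analyses of the two quality-of-life scales in the testing hierarchy. They could disagree with the mean-change results purely because missing data were handled differently.

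**Working it through.** The plan gives no figure to reproduce here, so the check compares the methods and then asks what can be said about size.

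**1. Handling of a subject who stops after Week 8**

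| Analysis | SAP section | Treatment at Week 12 |
|---|---|---|
| 5-D and Skindex-10 ANCOVA | 8.2.4.3 | Imputed from earlier visits, baseline and strata |
| 5-D and Skindex-10 MMRM | 8.2.4.3 | Not imputed; earlier visits inform the estimate through the model |
| NRS ≥4 and other cut-points | 8.2.4.3, 8.2.5.1 | Flag on the imputed dataset |
| NRS complete response | 8.2.5.1 | Non-responder |
| Skindex-10 ≥15, 5-D ≥5 | 8.2.5.2 | Absent from the model |

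SAP 8.2.4.1 and 8.2.4.2 say that missing data on these scales are handled either through the MMRM or by multiple imputation. The last row does neither.

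**2. Why this matters even under missing at random**

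A logistic model fitted to one visit is sound if missingness depends only on its own terms, such as treatment and baseline. If stopping depends on an earlier post-baseline score, data can still be missing at random given the history, but the single-visit model does not use that history. Imputation and the MMRM do.

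A simulation illustrates this. All inputs are assumptions: 10% to 16% missing at Week 12, response about 55% against 39%, within-subject correlation 0.7, and stopping that depends on the last observed score. The true difference was about 16 points.

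| Who leaves | Observed-case difference | Imputed from earlier visits |
|---|---|---|
| Poor responders in both arms | about 17 | about 16 |
| Poor responders on placebo only | about 13 | about 16 |
| Poor responders on CR845 only | about 20 | about 16 |

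The exact values depend on the dropout model chosen. The direction depends on which arm loses its poor responders.

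**3. Sensitivity to a low response among stoppers**

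Let p be the response rate among those observed, d the fraction missing and q the response rate among the missing. The all-randomized rate is (1 − d)p + dq. Assume p = 55% on CR845 and 40% on placebo, and q = 25% in both arms. The all-randomized difference is then

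0.15 − 0.30·d(CR845) + 0.15·d(placebo).

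- 15% missing on CR845, 10% on placebo: 0.150 − 0.045 + 0.015 = 0.120.
- 20% and 10%: 0.150 − 0.060 + 0.015 = 0.105.
- 5% and 15%: 0.150 − 0.015 + 0.0225 = 0.1575.

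The observed-case difference is 0.150 each time, so it can be too large or too small.

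A second illustration borrows the primary-endpoint planning values of SAP 2.6 (30% and 50%, 175 per arm), because none are given for these scales. The observed-case odds ratio is 2.33. If stoppers respond like stayers, nothing changes. If no stopper responds and dropout is 10% on placebo and 20% on CR845, about 158 and 140 subjects remain in the model. The all-randomized rates are 0.30 × 0.90 = 27% and 0.50 × 0.80 = 40%, a difference of 13 points. The odds ratio is (0.40/0.60)/(0.27/0.73) = 1.80.

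The cases in this step that set stoppers' response below stayers' describe departures from missing at random. They do not predict what the imputation of SAP 8.2.4.3 would give, because it assumes stoppers resemble other subjects in their arm, given their history.

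**4. How many are lost by week**

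The analyses are by week, so a stopper still counts at visits before stopping. If dropout rose linearly to an assumed 15% (15 × week/12), the fractions missing at Weeks 4, 8, 10 and 12 would be 5%, 10%, 12.5% and 15%.

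**The case against.** The best defence is that the SAP does state a rule, and that the rule is permitted. SAP 8.1.1 leaves missing data for other endpoints to their own sections, and SAP 3 allows denominators restricted to subjects with data. The imputed ANCOVA is used for Week 12 only; at other weeks the SAP reports these scores with a non-imputed MMRM, so non-imputed by-week responder rates follow the same pattern. The endpoints are listed among the other efficacy variables in SAP Table 3, outside the hierarchy, and SAP 3 makes their p-values descriptive.

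Most of this stands and limits the point. The parallel with the MMRM does not: a likelihood model over all visits accommodates dropout that is missing at random, and a separate logistic model at each visit does not.

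Three stronger readings are tempting, and the documents support none of them.

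- **A breach of intention-to-treat.** SAP 4.2 says "The ITT population will be used to analyze all efficacy endpoints collected during the double-blind phase". That names the analysis set; it does not require imputation, and SAP 3 allows non-missing denominators. The firmer ground is inconsistent handling.
- **Every early stopper is discarded.** Subjects are lost only at visits after stopping. Under SAP 3.1 a late early-termination visit can also map to Week 12 within +1/−3 days.
- **The CR845 effect will be overstated by some 3 points.** That comes from assuming 25% response among the missing and more loss on CR845. Reversing the imbalance reverses the sign, and the proposed imputation would not produce those rates by construction.

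**Conclusion.** The point holds as a question of consistency and possible bias in two supportive endpoints. SAP 8.2.5.2 leaves subjects without a total out of each visit's model, while the neighbouring analyses use their earlier data or count them as non-responders. No reason is given for the exception. The bias can favour or disfavour CR845 and can arise even if data are missing at random. Its size cannot be determined, because the documents give neither dropout rates nor responder rates for these scales; the figures above rest on assumed values.

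A reader might infer that the key secondary quality-of-life results are weakened. They are not: those tests use multiple imputation on all ITT subjects, and Type 1 error is untouched. Severity is low to moderate. The change is still worth making, because the material for a better analysis is already specified.

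**What to change.** Replace both no-imputation sentences in SAP 8.2.5.2, before unblinding:

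- Derive the ≥15-point and ≥5-point flags at each visit from the 20 imputed datasets of SAP 8.2.4.3, in which "the total score at each visit will be computed from the domain scores for each imputed dataset". Fit the logistic model in each and combine the results with MIANALYZE.
- Name the model covariates, which the section omits.
- Keep the observed-case proportions as a descriptive line, with the denominator for each arm and visit.
- Optionally add a version counting stoppers as non-responders, mirroring Sensitivity 1 in SAP 8.2.3. This would show how far the result depends on the missing-at-random assumption.

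The cost is small. No new imputation is needed, only some extra programming and one further rule. The sample code in SAP 14 bounds imputed values for the NRS only, so the SAP should say how imputed domain scores are bounded or rounded before the cut-points are applied.

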8.2.5.3 Patient Global Impression of Change

The PGIC is a global PRO measure that assesses the change (improvement or worsening) in overall status of itch relative to the start of the study. The scale has only 1 item, with values ranging from 1 (Very Much Improved) to 7 (Very Much Worse) (see protocol Appendix 5, Section 14.5).

Counts and percentages of subjects for each response will be reported as well as a count of subjects with missing values. All subjects should complete the PGIC Week 12 or early termination, so missing data should be minimal.

The counts and percentages of subjects who rate their itch condition as “Very much improved” or “Much Improved” at the end of Week 12 of the Double-blind Treatment Period/end of double-blind treatment, will be reported. Treatment difference will be tested using the Cochran-Mantel-Haenszel exact test, adjusting for the randomization stratification variables. The Mantel-Haenszel estimate of common odds ratio, exact 95% CI for the common odds ratio, and CMH exact test p-value will be reported for this treatment comparison. Additionally, the exact Clopper Pearson 95% CIs for the proportion of subjects who rate their itch condition as “Very much improved” or “Much Improved” will be reported.

9. SAFETY EVALUATION

9.1 Overview of Safety Analysis Methods

The following assessments will be used to evaluate the safety of CR845 in hemodialysis subjects with moderate-to-severe pruritus:

- Adverse events
- Clinical laboratory parameters
- Vital signs
- 12-lead ECG

All safety analysis will be performed based upon the treatment the subject actually received after randomization. All safety endpoints will be summarized by treatment group (and visit as appropriate). Safety analyses will be performed using the study population related to the analysis time period:

- Double-blind Treatment Period: Double-blind Safety Population
- Discontinuation Period: Double-blind Discontinuation Population for outcomes related to withdrawal symptoms and Double-blind Discontinuation Safety Population for all outcomes

9.2 Adverse Events

The period of adverse event reporting will start after the signing of the informed consent form (ICF) through the study Follow-up Visit or Early Termination Visit (or 7 days after the last dose if no Early Termination Visit was conducted). All adverse events that occur during this reporting period will be collected for all subjects, including subjects who are deemed to be screen failures.

Treatment-emergent adverse events (TEAEs) relative to the Double-blind Treatment Period are identified as any adverse event with an onset date after the first dose of the study drug up to the study End of Treatment/Early Termination Visit or the start of the Discontinuation Period or 7 days after the last dose if no End of Treatment/Early Termination Visit was conducted, whichever is later.

Adverse events that are considered “treatment-emergent” relative to the Discontinuation Period are identified as any adverse event with an onset date after the start of the Discontinuation Period through up to 2 weeks after this time point or the start of the Open-label Treatment Period, whichever comes first.

All tabular adverse event summaries will be for TEAEs by period.

For events with missing start dates, the following criteria will be used:

- If the start date for a particular event is missing, then the event is considered treatment-emergent for the Double-blind Treatment Period, unless the end date is reported and prior to the Double-blind Treatment Period start date.
- If a partial date is consistent with being in more than 1 period, then the ordering of assignment preference will be: Double-blind Treatment Period, Discontinuation Period, and Run-in Period. So if a partial date was consistent with the Double-blind Treatment Period and Discontinuation Period, it would be assigned to the Double-blind Treatment Period.
- If the start time is missing and the start date is the same as the start of a given period, the adverse event will be considered to have occurred in that period.

All adverse events will be coded to SOC and preferred term using the MedDRA version 20.1. The MedDRA treatment dictionary will be used to map adverse events verbatim to SOC and preferred term for standardization and summary purposes.

The incidence of TEAEs in each period will be summarized by treatment group and overall. If a subject experienced more than one episode of an adverse event, the subject is counted once for that preferred term. If a subject had more than 1 adverse event in a SOC, the subject is counted only once in that SOC. The summary tables will include incidence estimates for overall SOC, as well as for preferred terms within each SOC. Incidence for SOC will be presented by decreasing frequency overall and then alphabetically; for preferred terms, incidence will be presented by decreasing frequency overall within each SOC and then alphabetically.

The investigator is to record the severity of each adverse event as mild, moderate, or severe. If the same TEAE occurs for a subject on multiple occasions, the TEAE will be categorized according to the highest severity rating for that TEAE in that subject. If the severity of the TEAE is not reported, then the severity of the TEAE will be counted as severe. For each treatment group and period, the incidence within each category will be presented.

The investigator is to record their opinion on the relationship of each adverse event to study drug (not related, related). If a subject experiences the same adverse event multiple times, the event with the strongest relationship to study drug will be counted. For each treatment group, the incidence within each category will be presented. For the summary of TEAEs by relationship to study drug, if the relationship is missing, it will be counted as related. The incidence of drug-related events will be summarized for each period by treatment group and overall.

Separate tables summarizing the incidence of TEAEs of special interest (AESIs), will be presented for each study period. Selected preferred terms shown in Appendix 16.3 are combined into the following categories:

- Gait disturbance
- Fall
- Dizziness

- Somnolence
- Seizure
- Syncope
- Mental status changes
- Mood changes
- Unusual feeling, sensation
- Tachycardia
- Palpitation

Incidence rate will be calculated for AESIs, serious TEAEs, and TEAEs leading to death, and will be summarized by SOC and preferred term. Incidence rate will be calculated as $(1000 * \text{the number of events}) / \text{total person-years}$, where total person-years is the sum across all subjects in the treatment group of the individual subject risk times, and individual subject risk time is the number of days from first dose to the last day of the period where an event would be deemed to be treatment emergent.

The following summary tables will be presented for the Double-blind Treatment Period:

- An overall summary showing for each treatment group, the number and percentage of subjects with a TEAE, serious TEAE, related TEAE, severe TEAE, TEAE leading to dose interruption, TEAE leading to study drug discontinuation, TEAE leading to study discontinuation, TEAE of special interest. This table will also include number of events. This display will be repeated for subgroups by randomization stratification variables.
- TEAEs by SOC and preferred term
- Serious TEAEs by SOC and preferred term
- Severe TEAEs by SOC and preferred term
- TEAEs by SOC, preferred term, and maximum severity
- Related TEAEs by SOC and preferred term
- TEAEs leading to study drug discontinuation by SOC and preferred term
- SAEs by stratification factors, SOC, and preferred term
- Most common TEAEs ($\geq 2\%$ or more of subjects in any treatment group) by preferred term
- AESIs by preferred term
- Related AESIs by preferred term
- AESIs by stratification factors and preferred term
- AESI incidence rate by SOC and preferred term
- Serious TEAE incidence rate by SOC and preferred term

- TEAEs leading to death incidence rate by SOC and preferred term
- Custom MedDRA query (CMQ) events (see Section [16.2](#)).

Unless specified otherwise, the following summary tables will be presented for the Discontinuation Period based on the Discontinuation Period Safety population:

- An overall summary showing for each treatment group, the number and percentage of subjects with a TEAE, serious TEAE, related TEAE, severe TEAE, TEAE leading to study discontinuation, treatment emergent AESI. This table will also include number of events. This display will be repeated for subgroups by randomization stratification variables.
- TEAEs by SOC and preferred term (for Double-blind Discontinuation Population and Double-blind Discontinuation Safety Population)
- Serious TEAEs by SOC and preferred term
- TEAEs leading to study discontinuation by SOC and preferred term
- TEAEs potentially related to withdrawal by preferred term – see definition below (for Double-blind Discontinuation Population and Double-blind Discontinuation Safety Population)

Adverse events potentially related to withdrawal that occur during the 2-week Discontinuation Period will be identified based on a blinded review of the data using published criteria [[American Psychiatric Association 2013](#)]. First, subjects that have 3 or more AEs occurring within 6 days (which will include 3 dialysis visits) of the last dose of double-blind study drug from the list below programmatically will be selected for review:

1. Dysphoric mood
2. Nausea and/or vomiting
3. Muscle aches
4. Lacrimation and/or rhinorrhea
5. Pupillary dilation, piloerection, and/or sweating
6. Diarrhea
7. Yawning
8. Fever
9. Insomnia

The data for patients that have AEs potentially related to withdrawal (based on the above criteria) will be reviewed in a blinded fashion. Cases categorized as possibly related to withdrawal will be flagged and separate summaries will be produced for the Discontinuation Period and the Discontinuation Period Safety populations.

In addition, all adverse events will be listed in chronological order including subject identifier, age, race, gender, and all related event status information (start and stop dates, whether the event was ongoing, study day of onset, severity, seriousness, relationship to study drug, action taken with study treatment, and outcome). Note: For the all adverse event listing only, any screen failure subject who has an adverse event after signing ICF

will be included for completeness. Separate listings will be generated for serious adverse events (SAEs), deaths, and adverse events leading to treatment discontinuation. Additionally, a coding list of preferred terms and the verbatim text associated with them will be produced.

The incidence of TEAEs in each CMQ category (see Section [16.2](#)) will be summarized. If a subject experienced more than 1 episode of an adverse event, the subject is counted once for that preferred term; the total number of subjects reporting an event in the category will also be reported.

No statistical tests will be performed on adverse events.

